Genesis NICU is a Level II Regional Neonatology Center staffed full time by neonatologists from the University of Iowa Children's Hospital. The Genesis NICU provides family-centered treatment for babies born as early as 30 weeks gestation.

Participant Selection and Recruitment

The study will include 150 participants. There are no existing studies examining the time to diaper dermatitis for any treatment options (coconut oil or others), therefore, we conducted the simulation below to estimate a sample size that will have enough power to measure the primary outcomes in the study. The simulation generated time to discharge from a Gamma (3,2) and time to rash for coconut oil of Gamma (2,2) and standard Gamma (3,2). Patients that were discharged before getting diaper dermatitis were censored.

75 each Treatment: Gamma Scale 2 vs. 3, Shape = 2, p-value = 0.002.

The inclusion/exclusion criteria for the study is outlined below:

1. Inclusion criteria:
 - a. Babies admitted to the Genesis NICU
 - b. Anticipated stay in the NICU is ≥ 48 hours
 - c. Babies wearing diapers 24 hours a day
 - d. Parent willing to sign informed consent for the study
 - e. Parent willing to use the test products in the diaper area during the trial
 - f. Parent willing to not change the type or brand of diaper and wipes during the study
 - g. Parent willing to refrain from changing any other products whose use may have an effect of their baby's skin condition during the trial

2. Exclusion criteria:

- a. Babies with a gestational age <30 weeks
- b. Babies with major congenital malformations
- c. Active dermatological conditions other than diaper dermatitis that may affect trial results
- d. Known sensitivity to ingredients in trial products
- e. Babies whose parents have a hazelnut or coconut allergy
- f. Babies whose mother is <18 years of age
- g. Other severe acute medical conditions that may increase the risk associated with trial participation

3. Recruitment

[figure not shown]

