The Standard of Care group will receive the current standard of care for diaper dermatitis. The standard of care is no treatment until a diaper dermatitis appears. If diaper dermatitis appears, participants will receive a generous layer of Medline Remedy Phytoplex Z-Guard Skin Protectant, which is an over-the-counter skin protectant with the following active ingredients: white petrolatum 57% and zinc oxide 17%. The participants will also be switched from using Pampers Sensitive wipes to a dry washcloth and water, per the standard of care.

The primary safety endpoint for this study will be skin that is eroded and/or blistered in the diaper area with bleeding. If a participant reaches the primary safety endpoint their study participation will be complete and additional diaper dermatitis treatment options can be used, per currently available treatment options in the Genesis NICU.

The research staff will conduct a quality check each week using a sample of participant rooms to ensure the participants continue to receive care based on the study arm they were assigned to and the diaper dermatitis logs are being completed for every diaper change.

Study Outcomes

Primary Outcomes:

1. The number of days free from diaper dermatitis, as measured by the diaper dermatitis log.
2. The number of participants that develop adverse effects.

Secondary Outcomes:

3. For participants that develop diaper dermatitis, the number of days with diaper dermatitis (duration of diaper dermatitis).
4. For participants that develop diaper dermatitis, the number of days until the participant reaches the primary endpoint (skin eroded and/or blistered with bleeding), as measured by the diaper dermatitis log.
5. The level of parent satisfaction with the diaper dermatitis treatment used, as measured by the parent satisfaction survey.

The study outcomes will be collected for all participants and comparisons will be made between the two study arms.

Data Collection

Every Diaper Change

The nursing staff or Clinical Research Coordinator in the Genesis NICU will collect information about diaper dermatitis at every diaper change using the diaper dermatitis log. The following information will be included in the log:

1. Date
2. Time
3. Presence of pink or red skin¹¹
4. Presence of pimply areas on the skin.¹¹
5. Presence of eroded and/or blistered skin with bleeding (primary safety endpoint)¹¹

Discharge

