Expected	Any adverse event that is identified in nature, severity or frequency in the study protocol. Any adverse event that is previously known or anticipated to result from the underlying disease, disorder, or condition of the subject(s).
Unexpected	Any adverse event occurring in one or more subjects participating in the study, the nature, severity, or frequency of which is not consistent with either: 
 1. The known or foreseeable risks associated with the study procedures that are described in the protocol 2. The expected natural progression of any underlying disease, disorder, or condition of the subject(s) experiencing the adverse event and the subject's predisposing risk factor profile for the adverse event.

The Clinical Research Coordinator will assess adverse events on a weekly basis for this study by reviewing patient medical records. Serious adverse events will also be identified by nursing staff on the NICU and will be reported to the Clinical Research Coordinator. The Clinical Research Coordinator will report SAEs to [name] (Principal Investigator) to determine the need for additional treatment. Adverse events that meet the criteria outlined by the Genesis IRB (i.e., events that are unanticipated, serious or anticipated that occur with greater frequency or severity than expected) will be reported to the Genesis IRB within 10 working days after becoming aware of the information, as per Genesis IRB Standard Operating Procedures.

Data Analysis

Once data is transferred to the GHS Biostatistics Group, research team members will double enter the data and manage the databases, assign identification numbers to participants, perform edit diagnostics and prepare worksheets for analysis.

Comparative analyses of Coconut Oil and Standard of Care groups will include exact tests for comparing binomial characteristics, stochastic ordering for ordinal distributions (exact

permutation tests) and Wilcoxon rank sum tests for continuous factors. All will be analyzed with Cytel Studio StatXact Analyses.

Initially, data will be presented as a Kaplan-Meier plot of time to rash for the log-rank comparison of standard treatment and coconut oil. This will provide the probability of rash by treatment on any given day after the start of the study.

Cox proportional analyses will be used to control for risk factors to determine whether they are effect modifiers or confounders of the treatment effect.

Data Management

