Data will be stored in a locked filing cabinet within the Principal Investigator's office in the Genesis NICU and with the Clinical Research Coordinator in the Clinical Research office at Genesis Medical Center East Campus. Once all data is transferred to the GHS Biostatistics Group for data analysis, it will be coded and stored in a secure database. The code linking the participant names and identification numbers will be secured at the GHS Biostatistics Group and only research team members will have access to the code. All research team members have completed NIH Human Subjects Protection training and are committed to protecting the confidentiality of participants and following HIPAA guidelines.

Quality Assurance, Monitoring, & Safety

A Data and Safety Monitoring Board will be convened to oversee this study. The Board will meet at the start of the study and at least bi-annually to review adverse events and the study data. All adverse events will be reported promptly to the Data and Safety Monitoring Board and the Genesis IRB.

References

3. Lund, C. H., Kuller, J., Lane, A. T., Lott, J. W., Raines, D. A., & Thomas, K.K. Neonatal skin care: Evaluation of the AWHONN/NANN research-based practice project on knowledge and skin care practices. *Journal of Obstetric, Gynecologic and Neonatal Nursing* 2001; 30(1): 30-40.

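### Adverse effects are a primary outcome, but mild ones have no prompted, prospective collection: weekly chart review can count only what staff happened to chart

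*Protocol*

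**What the plan says.** The Protocol's Study Outcomes section lists, as the second primary outcome, "The number of participants that develop adverse effects". Identifying the adverse effects of coconut oil is the second primary objective. The SAP repeats both.

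The Safety Reporting section of both documents gives the method: "The Clinical Research Coordinator will assess adverse events on a weekly basis for this study by reviewing patient medical records". A second route exists for serious events only: "Serious adverse events will also be identified by nursing staff on the NICU and will be reported to the Clinical Research Coordinator".

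The Risks section names the effects the study will track:
- worsening rash, eczema, and skin inflammation or swelling;
- yeast infection;
- cough, runny nose, watery eyes, skin redness and discomfort;
- diarrhea.

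The diaper log (Data Collection) is completed at every change. It has three clinical items: pink or red skin, pimply areas, and eroded or blistered skin with bleeding. It is not named as a source of adverse events. After recruitment closes, a chart pull collects infection and medications among other variables. No adverse-event form, bedside checklist, discharge assessment or post-discharge contact is described.

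The Quality Assurance section adds: "All adverse events will be reported promptly to the Data and Safety Monitoring Board and the Genesis IRB". Safety Reporting instead sends to the IRB the events that meet IRB criteria, within 10 working days of becoming aware of them.

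**The concern.** A count of participants with adverse effects is only as complete as the process that looks for them. Under the protocol's severity scale a mild event needs no intervention, so it generates no order and no drug and may leave no trace in the chart unless someone is prompted to write it down. Nothing in the plan prompts anyone, except for the three skin signs on the log.

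The trial is also unmasked. The coordinator draws the envelope, places the product in the room, tells the parents and the charge nurse the arm, and later reads the charts for adverse events. Unprompted charting by staff who know the arm could differ between arms in either direction. A finding of few adverse effects with coconut oil could then not be told apart from few effects having been written down.

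Timing is a second and separate matter. A weekly review in a population with short stays will often take place after the baby has gone home, when the baby can no longer be examined and recurrence on re-application, one of the protocol's relatedness criteria, can no longer be observed in the unit.

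**Working it through.** **Coverage of the tracked effects.** Setting the Risks list against the stated capture routes:

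| Tracked effect | Prompted at the bedside? | Other route |
|---|---|---|
| Skin redness, worsening rash | Yes, at least in part, through the log | Weekly chart review |
| Yeast infection | No | Weekly chart review; infection item in the end-of-study chart pull |
| Eczema, swelling, cough, runny nose, watery eyes, discomfort, diarrhea | No | Weekly chart review, if charted |
| Any serious event | Nurses identify and report | Weekly chart review |

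For the third row, a non-serious effect enters primary outcome 2 only if routine charting mentioned it. The documents give no charting rate, so the under-count cannot be calculated.

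**Delay until review.** The plan states no figure for this, so there is none to reproduce. The inputs are:
- Time to discharge T is simulated as Gamma (3,2) (Participant Selection and Recruitment). Units are not stated; days are assumed.
- Parameter order is ambiguous, since the result line reads "75 each Treatment: Gamma Scale 2 vs. 3, Shape = 2, p-value = 0.002". Both orders, shape 3 with scale 2 and shape 2 with scale 3, have mean 6. Reading the second figure as a rate gives a mean stay of 1.5 days, at odds with the entry criterion "Anticipated stay in the NICU is ≥ 48 hours".
- The review interval is 7 days. The plan does not say whether it is a fixed weekday or each baby's own clock. A fixed weekday with random enrolment day is assumed first.
- Events are assumed to fall uniformly over the stay.
- The sample size is 150.

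*Step 1, stays shorter than a week.* P(T < 7) = 0.679 (shape 3, scale 2) or 0.677 (shape 2, scale 3). Among stays of at least 2 days it is 0.651 or 0.622.

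*Step 2, no review during the stay.* A stay of T days misses a fixed weekly review with probability max(0, 1 - T/7), so the share is 1 - E[min(T,7)]/7.
- Shape 3, scale 2: 1 - 5.026/7 = 0.282, or 0.282 × 150 ≈ 42 babies.
- Shape 2, scale 3: 1 - 4.739/7 = 0.323, or 0.323 × 150 ≈ 48 babies.
- Among stays of at least 2 days: 0.24 under either order.

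*Step 3, event first reviewed after discharge.* An event with R days of stay remaining is reviewed late with probability max(0, 1 - R/7). With R uniform on (0, T) and m = min(T,7), this averages to (m - m²/14)/T for a stay of T days.
- Each baby weighted equally: 0.60 and 0.61.
- Each day of stay weighted equally: 0.49 and 0.47.

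*Step 4, sensitivity.*

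| Setting | No review during stay | Events first reviewed after discharge |
|---|---|---|
| Mean 6 days, fixed weekday | 28-32% | 47-61% |
| Mean 6 days, review every 7 days on each baby's own clock | 68% | 55-75% |
| Mean 12 days (assumed: shape 3 scale 4, or shape 2 scale 6), fixed weekday | 8-13% | 27-41% |

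The range for late review spans both parameter orders and both weightings.

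**The case against.** The strongest reply is that a medical record persists. Nothing in either document says review stops at discharge, and for a count of participants a charted event is the same whether it is read on day 3 or day 9. This stands. A reader might infer that, because about two thirds of simulated stays are under a week, many effects are never recorded. The documents do not support that: the interval delays reading and does not erase what was charted. The percentages above measure delay, not under-counting.

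Nor does a stay under 7 days mean that no review takes place. On a fixed weekday about 70% of babies would have at least one review while in the unit.

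The diaper area is not unobserved either. Redness, pimply areas and eroded or blistered skin are logged at every change, and research staff check log completion weekly in a sample of rooms. Serious events have a second route, and infection is abstracted at the end. These points also stand, and they narrow the gap to the effects that no form asks about. Relatedness can often be judged from records, because the criteria turn largely on alternative causes; only the recurrence criterion needs the baby still under treatment.

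The discharge distribution was chosen for a sample-size simulation and is not an estimate of stay in this unit. This is fair, and it is why the 12-day row is shown.

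Finally, one might read weekly detection as contradicting prompt reporting. It does not: prompt reporting can run from awareness. The mismatch that remains is in which events are reported and how fast.

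**Conclusion.** The concern holds for collection. A primary outcome has no prompted, prospective record for most of the non-serious effects the protocol says it will track. The likely loss is of mild effects that nobody charts. Its size is unknown, and with unmasked care it need not be equal in the two arms.

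The timing point is secondary and conditional. With simulated stays read in days (mean 6), a fixed weekly review day and uniform event timing, 28-32% of babies have no review during their stay, and 47-61% of events are first reviewed after discharge. With an assumed mean of 12 days the figures are 8-13% and 27-41%. The absence of a bedside prompt does not depend on any of these assumptions.

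The two statements on reporting differ in scope (events meeting IRB criteria against all adverse events) and in speed (10 working days from awareness against promptly), and must be reconciled.

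**What to change.** 1. Add the Risks list to the existing diaper log as a once-daily yes/no checklist, identical in both arms.
2. Make an adverse-event review due for every participant at or before discharge, and weekly as well for longer stays.
3. State that primary outcome 2 is counted from this record, and say whether the log's existing skin items count as adverse events.
4. Reconcile the Safety Reporting and Quality Assurance sections on which events go to the Board and the IRB, and how fast.

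The first three use a form already in use and a time at which the parent survey is already handed out. They are not free. Nurses spend a little more time each day. Nursing staff may hand out the survey, so a coordinator is not necessarily present at discharge and the review has to be scheduled. More mild events will be recorded in both arms. The change works only prospectively, because uncharted effects cannot be recovered later.

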## Introduction/Background

Diaper dermatitis is an inflammatory reaction of the skin in the perineal area of infants, and is a common pediatric condition. It can have many causes including infection (yeast, bacterial or viral), friction irritation, skin sensitivity to urine and/or feces, and allergies (perfumes). The overall incidence of diaper dermatitis in infants is estimated to be between 7% and 35%. Diaper dermatitis is often a result of increased moisture due to contact with urine and feces, followed by friction. Urine contact with diapered skin raises the skin pH, thus increasing skin permeability and activating fecal enzymes, which are known irritants that can cause skin breakdown. Skin breakdown encourages secondary skin infections that increases the challenge of managing diaper dermatitis. Diaper dermatitis can range in severity from generalized erythema (redness of the skin) to open wounds, and can cause significant pain for babies and distress for parents.

Premature infants have been found to be at higher risk for diaper dermatitis due to their age, and varying degrees of underdeveloped skin structures and functions. In addition, babies that are ill have a higher risk due to increased incidence of diarrhea, cancer, gastrointestinal anomalies, neurological disorders, genetic syndromes and malnutrition. Genesis Neonatal Intensive Care Unit (NICU) infants are often on a number of antibiotics that cause diarrhea, which significantly contributes to the challenges Genesis faces with diaper dermatitis. Genesis estimates its incidence of diaper dermatitis in the NICU is approximately 50%.

The current practice of preventing and treating diaper dermatitis is inconsistent and often not evidence-based. One comprehensive literature review supports treatment of diaper dermatitis through frequent diaper changes, use of super absorbent diapers and protection of the perineal skin with a product containing petrolatum and/or zinc oxide. While numerous studies have established guidelines for neonatal skin care, they often use products that contain numerous chemicals. Due to the increasing problem with bioaccumulation of numerous chemicals in the environment and increased exposure in infants and children, the National Association of Neonatal Nurses has encouraged the removal of chemicals in the NICU. Following this recommendation, Genesis is interested in examining the safety and effectiveness

of using unrefined, organic coconut oil for the prevention and treatment of diaper dermatitis among NICU babies at Genesis Medical Center, Davenport.

Coconut oil is the fatty oil obtained from the dried, solid part of the endosperm of *Cocos Nucifera*. It is a mixture of mainly saturated fatty acids (medium chain triglycerides), with lauric acid being the most abundant. In vitro and in vivo research has provided evidence that lauric acid is effective at killing a wide variety of gram-positive and gram-negative bacteria and *Candida* species. This suggests coconut oil may be an effective anti-fungal to treat diaper dermatitis caused by bacteria. The fatty acids in coconut oil may also act as an effective barrier for skin irritants. Coconut oil has been shown to have a low risk of allergic reaction or adverse effects when applied topically. There have been no published clinical trials on the effectiveness of coconut oil in preventing or treating diaper dermatitis in infants. The majority of research regarding the use of coconut oil in neonates centers around massage.

Studies have shown that coconut oil can be absorbed through the skin of neonates, without any negative side effects. One randomized, controlled study found preterm babies massaged with coconut oil daily for 31 days had significantly higher weight gain velocity compared to mineral oil and placebo, and higher length gain velocity compared to placebo. Other studies have found coconut oil to be an effective treatment for atopic dermatitis in pediatric and adult patients. One randomized controlled trial of 117 pediatric patients found topical application of virgin coconut oil for eight weeks was superior to that of mineral oil based on clinical (SCORing of Atopic Dermatitis [SCORAD]) and instrumental (transepidermal water loss [TEWL], skin capacitance) assessments. Another double-blind controlled trial of 52 adults found virgin coconut oil was significantly more effective than virgin olive oil at reducing the prevalence of *Staphylococcus aureus* (RR=0.10, p=0.0028), indicating coconut oil may have an antimicrobial effect.

## **Purpose/Objectives**

The purpose of the study is to examine the safety and effectiveness of the use of coconut oil for the prevention and treatment of diaper dermatitis among NICU babies at Genesis Medical Center, Davenport.

### **Primary objectives:**

1. To determine and compare the number of days free of diaper dermatitis (“time to rash”) within and between the two treatment groups (i.e., coconut oil and standard of care)
2. To identify the adverse effects of coconut oil when used as a barrier cream for the prevention and treatment of diaper dermatitis

### **Secondary objectives:**

[figure not shown]
3. To determine and compare the duration of diaper dermatitis within and between the two treatment groups.
4. To determine and compare changes in diaper dermatitis severity within and between the two treatment groups.
5. To determine and compare parent satisfaction scores within and between the two treatment groups at discharge.

## Study Design

This is a prospective, randomized controlled trial to examine the effect of coconut oil on the prevention and treatment of diaper dermatitis in NICU babies at Genesis Medical Center, Davenport. The study will be carried out in the Genesis Medical Center, Davenport NICU. The Genesis NICU is a Level II Regional Neonatology Center staffed full time by neonatologists from the University of Iowa Children's Hospital. The Genesis NICU provides family-centered treatment for babies born as early as 30 weeks gestation.

## Participant Selection and Recruitment

The study will include 150 participants. There are no existing studies examining the time to diaper dermatitis for any treatment options (coconut oil or others), therefore, we conducted the simulation below to estimate a sample size that will have enough power to measure the primary outcomes in the study. The simulation generated time to discharge from a Gamma (3,2) and time to rash for coconut oil of Gamma (2,2) and standard Gamma (3,2). Patients that were discharged before getting diaper dermatitis were censored.

The inclusion/exclusion criteria for the study is outlined below:

1. Inclusion criteria:
  - a. Babies admitted to the Genesis NICU
  - b. Anticipated stay in the NICU is  $\geq 48$  hours
  - c. Babies wearing diapers 24 hours a day

- d. Parent willing to sign informed consent for the study
- e. Parent willing to use the test products in the diaper area during the trial
- f. Parent willing to not change the type or brand of diaper and wipes during the study
- g. Parent willing to refrain from changing any other products whose use may have an effect of their baby's skin condition during the trial

2. Exclusion criteria:

- a. Babies with a gestational age <30 weeks
- b. Babies with major congenital malformations
- c. Active dermatological conditions other than diaper dermatitis that may affect trial results
- d. Known sensitivity to ingredients in trial products
- e. Babies whose parents have a hazelnut or coconut allergy
- f. Other severe acute medical conditions that may increase the risk associated with trial participation

[figure not shown]
3. Recruitment

[figure not shown]
Participants will be recruited from the Genesis NICU. Each day the nursing staff will identify babies and parents that meet the inclusion/exclusion criteria. The nursing staff will notify the Genesis Clinical Research Coordinators (CRC) of eligible participants. The CRCs will also be screening the NICU patient lists to identify newly admitted babies. The CRC will approach the eligible participants to discuss the study and informed consent. The participants will have up to 24 hours to review the informed consent and decide whether or not to participate.

Genesis estimates that approximately 200 – 250 babies are admitted to the NICU annually, which suggests that it is feasible to enroll 150 babies in approximately 1.5 years for this study. The estimated accrual rate is 8 babies per month. The research team will be reviewing the accrual rate on a monthly basis. If recruitment is slower than expected, the team will examine the reasons for slow recruitment and make adjustments, as needed. Any changes to recruitment procedures will be presented to the IRB before implementation.

